6.3. Duration of Follow Up

6.3.1. Patients will be followed for toxicity for 14 days after treatment has been discontinued or until progression/death, whichever occurs first

7. DOSING DELAYS / DOSE MODIFICATIONS

- 7.1. If serum ketosis is not obtained (BHB ≥ 0.5 mM), the RD will review the daily food diary (Appendix II) to determine if the calculation of net carbohydrate intake is accurate and to modify the diet to obtain ketosis.
- 7.2. If patient develops Grade 3 or Grade 4 toxicity determined to be related to the diet then patient will be removed off diet. Toxicity can be determined by research coordinator, primary investigator or co-investigator.
- 7.3. If patient has a fasting glucose level >90 mg/dl, it will precipitate an evaluation of dietary intake and/or medical issues (i.e. infection).
- 7.4. If patient is admitted to the hospital while on study/diet, compliance with the diet will be up to the admitting physician and the patient. If the admission is secondary to the diet/protocol, this will be documented as a serious adverse event and the diet will be discontinued to till patient returns to Grade 1 level and then the diet can be resumed. If the patient has a second serious adverse event from the protocol, then the patient will be permanently removed from the diet. Please see section 6.2

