6.2. **Duration of Therapy:** In the absence of treatment delays due to adverse events, treatment may continue for 10-11 weeks or until one of the following criteria applies:

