6.2.1. Intercurrent illness that prevents further administration of treatment

6.2.2. Unacceptable adverse treatment related toxicity, NCI CTC AE version 4.0. Grade 3 or 4 that fails to recover to baseline or < Grade 3 in the absence of treatment within 4 weeks

6.2.3. General or specific changes in the patient’s condition that render the patient unable or unsuited for further participation in the judgment of the investigator,

6.2.4. Patient decision to withdraw from treatment (partial consent) or from the study (full consent),

6.2.5. Pregnancy during the course of the study for a childbearing participant.

6.2.6. Death.

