8.3. Definitions

8.4.1. **Adverse Event:** An **adverse event** (AE) is any unfavorable or unintended event, physical or psychological, associated with a research study, which causes harm or injury to a research participant as a result of the participant's involvement in a research study. The event can include abnormal laboratory findings, symptoms, or disease associated with the research study. The event does not necessarily have to have a causal relationship with the research, any risk associated with the research, the research intervention, or the research assessments. Adverse events may be the result of the interventions and interactions used in the research; the collection of identifiable private information in the research; an underlying disease, disorder, or condition of the subject; and/or other circumstances unrelated to the research or any underlying disease, disorder, or condition of the subject.

8.4.2. **Serious Adverse Events:** A **serious adverse event** (SAE) is any adverse experience occurring at any dose that results in any of the following outcomes:

- 8.4.2.1. Results in **death**.

8.4.2.2. Is a **life-threatening** adverse experience. The term life-threatening in the definition of serious refers to an adverse event in which the subject was at risk of death at the time of the event. It does not refer to an adverse event which hypothetically might have caused death if it were more severe.

8.4.2.3. Requires **inpatient hospitalization or prolongation of existing hospitalization**. Any adverse event leading to hospitalization or prolongation of hospitalization will be considered as Serious, UNLESS at least one of the following expectations is met:

- 8.4.2.3.1. The admission results in a hospital stay of less than 24 hours OR
- 8.4.2.3.2. The admission is pre-planned (e.g., elective or scheduled surgery arranged prior to the start of the study) OR
- 8.4.2.3.3. The admission is not associated with an adverse event (e.g., social hospitalization for purposes of respite care).
- 8.4.2.3.4. However it should be noted that invasive treatment during any hospitalization may fulfill the criteria of “medically important” and as such may be reportable as a serious adverse event dependent on clinical judgment. In addition where local regulatory authorities specifically require a more stringent definition, the local regulation takes precedent.

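### Sections 7.2 and 7.4 both govern a first diet-related Grade 3-4 event with admission and are not reconciled; short admissions are classed two ways, and the hypoglycaemia limit in 9.2 is printed in mg/L

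*Combined protocol and SAP*

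**What the plan says.** **Diet stopping.** Section 7.2 reads: "If patient develops Grade 3 or Grade 4 toxicity determined to be related to the diet then patient will be removed off diet". It sets no condition for return and does not say how long the removal lasts.

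Section 7.4 deals with hospital admission. On diet-related admissions it says: "If the admission is secondary to the diet/protocol, this will be documented as a serious adverse event". The diet then stops until the "patient returns to Grade 1 level and then the diet can be resumed". It continues: "If the patient has a second serious adverse event from the protocol, then the patient will be permanently removed from the diet". The section closes with a pointer to 6.2 and does not mention 7.2.

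**Ending treatment.** Section 6.2 says that "treatment may continue for 10-11 weeks or until one of the following criteria applies". Criterion 6.2.2 is unacceptable treatment-related toxicity of "Grade 3 or 4 that fails to recover to baseline or < Grade 3 in the absence of treatment within 4 weeks". Criterion 6.2.3 covers a patient who becomes "unable or unsuited for further participation in the judgment of the investigator".

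**Seriousness.** In the SAE definition, 8.4.2.3 counts an adverse event leading to hospitalization as serious unless an exception applies. The first exception, 8.4.2.3.1, is: "The admission results in a hospital stay of less than 24 hours". Sections 8.4.2.3.4 and 8.4.2.6 leave room for judgment on medically important events. Section 8.6 requires the principal investigator to report every SAE to the DSMB and IRB within 24 hours of learning of it.

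**Glucose.** Section 9.2 gives the hypoglycaemia limit for safety monitoring as below 70 mg/L. Section 7.3 sets its fasting-glucose trigger at above 90 mg/dl.

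**The concern.** These rules decide what happens to a patient harmed by the study diet. As written, two careful readers could handle the same first event differently. One takes the patient off the diet under 7.2 and finds no stated way back. The other holds the diet under 7.4 and may restart it at Grade 1.

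The SAE definition adds a second ambiguity. Permanent removal under 7.4 depends on counting SAEs, and fast reporting under 8.6 depends on an event being an SAE. For short diet-related stays, 7.4 and 8.4.2.3.1 can give different answers to that question.

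The 9.2 limit is the only hypoglycaemia threshold in the document and is stated to be for patient safety. Its unit differs from the one used for glucose in 7.3.

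**Working it through.** No sample size, power or error rate is involved. The check is a side-by-side reading and one unit conversion.

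**1. Do 7.2 and 7.4 overlap?** The trigger in 7.2 is a Grade 3 or 4 toxicity related to the diet, whether or not the patient is admitted. The trigger in 7.4 is an admission caused by the diet, with no grade limit. A first diet-related Grade 3-4 event that leads to admission meets both.

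**2. What does each rule then say?**
- 7.2: off the diet. Duration and return are not stated.
- 7.4: off the diet until Grade 1, after which resumption is allowed but not required. Removal is permanent at the second SAE.

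Neither rule cites the other, and no other passage ranks them. The only precedence wording in the safety sections (8.4.2.3.4) concerns local regulation on the SAE definition.

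**3. Does the pointer to 6.2 settle it?** The duration in 6.2 fits the diet: day -7 to about day 70 is 77 days, and 77 / 7 = 11 weeks. So 6.2.2 can be read as covering the diet. It differs from 7.4 in three ways:
- *Threshold:* 6.2.2 looks for baseline or below Grade 3; 7.4 looks for Grade 1.
- *Time limit:* 6.2.2 allows 4 weeks off treatment; 7.4 sets none.
- *Function:* 6.2.2 says when treatment ends; 7.4 says when the diet may restart.

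Take a patient whose event has fallen to Grade 2 within 4 weeks. Criterion 6.2.2 does not end treatment, 7.4 does not yet allow the diet to resume, and 7.2 has removed the patient with no further instruction. The pointer adds a third threshold and does not say which rule governs.

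**4. SAE status of a short admission.** Take a diet-related stay under 24 hours that meets no other seriousness criterion.
- Under 7.4 it is an SAE. It counts as the first, and the 24-hour report in 8.6 is due.
- Under 8.4.2.3.1 it is not serious through hospitalization. It does not count, and that report is not triggered.

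If the same patient later has a longer diet-related admission, that admission is the second SAE on the first reading (permanent removal). On the second reading it is the first SAE (stop, with resumption allowed).

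**5. Glucose unit.** Inputs: 70 mg/L (9.2), 90 mg/dl (7.3), 1 L = 10 dl.
- 9.2 as printed: 70 mg/L / 10 = 7 mg/dl.
- The same number in the unit of 7.3: 70 mg/dl × 10 = 700 mg/L, and 700 / 70 = 10.
- The 7.3 trigger in the unit of 9.2: 90 × 10 = 900 mg/L, and 900 / 70 = 12.9 times the printed 9.2 limit.

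No hold, report or other action is attached to the 9.2 value.

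**The case against.** The strongest reply is that 7.2 and 7.4 can be read together. Section 7.2 does not say the removal is permanent, while 7.4 uses that word for a second SAE only. Section 7.4 is permissive about resuming. A patient taken off and never restarted satisfies both passages, and so does one taken off and restarted at Grade 1. On this view 7.2 is the general step, 7.4 is the specific rule for admissions, and 6.2.2 is the outer limit, which itself contemplates an interruption that need not be final.

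Much of this stands. A reader might infer that 7.2 orders permanent removal and so flatly contradicts 7.4; the text does not support that. What remains is that the compatible reading has to be inferred. The plan does not state it, and 6.2.2 and 7.4 still use different recovery thresholds.

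A Grade 3-4 event without admission is also not a contradiction. Only 7.2 directs it, and the absence of a restart rule there is missing detail.

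On short stays, 7.4 can be read as the specific rule that overrides the general exemption, and the judgment routes in 8.4.2.3.4 and 8.4.2.6 may make some of them serious anyway. That narrows the problem to stays that meet no other criterion, but the plan does not say that 7.4 overrides.

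The mg/L entry may be a simple slip, and the trigger that prompts action (7.3) is in mg/dl. No operational effect is shown. It is still the only stated hypoglycaemia limit.

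Investigator discretion (6.2.3), the weekly study team review and DSMB oversight limit the harm. They do not supply the missing rule.

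**Conclusion.** The point holds as a failure to reconcile safety rules, not as a proven contradiction between them. For a first diet-related Grade 3-4 event with admission, 7.2 and 7.4 both apply, their relation is unstated, and 6.2.2 does not supply it. For a diet-related stay under 24 hours that meets no other seriousness criterion, the count toward a second SAE and the 24-hour report depend on the passage followed. The 9.2 limit as printed is 7 mg/dl, one tenth of the same number in the unit of 7.3.

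Apart from that factor of 10, nothing can be sized. The documents give no expected rate of such events and no length of a diet hold, so neither the number of patients affected nor the diet time at stake is derivable. A reader might also infer an effect on the ketosis rate or on compliance. The documents do not support a figure for either, and section 10.2.5 gives compliance no numeric definition.

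The conclusion rests on the wording of the cited sections and on no outside assumption.

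**What to change.** The investigators should:

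1. Reconcile 6.2.2, 7.2 and 7.4 into one stated rule for diet-related Grade 3-4 events, saying how the passages relate and whether and when a restart applies. It would help to cover events without admission in the same text.
2. Make 7.4 and 8.4.2.3.1 agree on when a diet-related admission is an SAE, for both the count toward a second SAE and the 24-hour report in 8.6.
3. Put the glucose limits in 9.2 and 7.3 in one unit and confirm the 9.2 value.

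As a clerical matter, the template wording on attribution in 8.5.2.3 and 8.5.2.4, which speaks of a study drug, can be adapted to the diet in the same amendment.

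The choice of clinical rule and of glucose limit stays with the investigators. The cost is a protocol wording amendment, with no added visits, procedures or patients.

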8. ADVERSE EVENTS: LIST AND REPORTING REQUIREMENT

8.1. Adverse Events and Potential Risks with Dose Modifications

8.2. Modified Atkins Diet

- 8.2.1. Immediate short-term potential adverse effects^{xi}
 - 8.2.1.1. Constipation
 - 8.2.1.2. Exacerbation of gastroesophageal reflux disease
 - 8.2.1.3. Fatigue
 - 8.2.1.4. Food refusal
 - 8.2.1.5. Dehydration
 - 8.3.1.6. Nausea
 - 8.4.1.7. Mild increase in total cholesterol

8.3. Definitions

8.4.1. **Adverse Event:** An **adverse event** (AE) is any unfavorable or unintended event, physical or psychological, associated with a research study, which causes harm or injury to a research participant as a result of the participant's involvement in a research study. The event can include abnormal laboratory findings, symptoms, or disease associated with the research study. The event does not necessarily have to have a causal relationship with the research, any risk associated with the research, the research intervention, or the research assessments. Adverse events may be the result of the interventions and interactions used in the research; the collection of identifiable private information in the research; an underlying disease, disorder, or condition of the subject; and/or other circumstances unrelated to the research or any underlying disease, disorder, or condition of the subject.

8.4.2. **Serious Adverse Events:** A **serious adverse event** (SAE) is any adverse experience occurring at any dose that results in any of the following outcomes:

- 8.4.2.1. Results in **death**.

8.4.2.2. Is a **life-threatening** adverse experience. The term life-threatening in the definition of serious refers to an adverse event in which the subject was at risk of death at the time of the event. It does not refer to an adverse event which hypothetically might have caused death if it were more severe.

8.4.2.3. Requires **inpatient hospitalization or prolongation of existing hospitalization**. Any adverse event leading to hospitalization or prolongation of hospitalization will be considered as Serious, UNLESS at least one of the following expectations is met:

- 8.4.2.3.1. The admission results in a hospital stay of less than 24 hours OR
- 8.4.2.3.2. The admission is pre-planned (e.g., elective or scheduled surgery arranged prior to the start of the study) OR
- 8.4.2.3.3. The admission is not associated with an adverse event (e.g., social hospitalization for purposes of respite care).
- 8.4.2.3.4. However it should be noted that invasive treatment during any hospitalization may fulfill the criteria of “medically important” and as such may be reportable as a serious adverse event dependent on clinical judgment. In addition where local regulatory authorities specifically require a more stringent definition, the local regulation takes precedent.

8.4.2.4. Results in persistent or significant disability/incapacity. The definition of disability is a substantial disruption of a person’s ability to conduct normal life’s functions.

8.4.2.5. Is a congenital anomaly/birth defect.

8.4.2.6. Is an important medical event. Important medical events that may not result death, be life-threatening, or require hospitalization may be considered a serious adverse experience when, based upon appropriate medical judgment, they may jeopardize the subject and may require medical or surgical intervention to prevent one of the outcomes listed in this definition. Examples of such medical events include allergic bronchospasm requiring intensive treatment in an emergency room or at home, blood disease or disorders, or convulsions that do not result in inpatient hospitalization, or the development of drug dependency or drug abuse. The development of a new cancer is always considered an important medical event.

8.4. Adverse Event Evaluation: The investigator or designee is responsible for ensuring that all adverse events (both serious and non-serious) observed by the clinical team or reported by the subject which occur after the subject has signed the informed consent are fully recorded in the subject’s medical records. Source documentation must be available to support all adverse events. A laboratory test abnormality considered clinically relevant (e.g., causing the subject to withdraw from the study, requiring treatment or causing apparent clinical manifestations, result in a delay or dose modification of study treatment, or judged relevant by the investigator), should be reported as an adverse event.

8.5.1. The investigator or sub-investigator (treating physician if applicable) will provide the following for all adverse events (both serious and non-serious):

- 8.5.1.1. Event term (as per CTCAE)

- 8.5.1.2. Description of the event
- 8.5.1.3. Date of onset and resolution
- 8.5.1.4. Expectedness of the toxicity
- 8.5.1.5. Grade of toxicity
- 8.5.1.6. Attribution of relatedness to the investigational agent- (this must be assigned by an investigator, sub-investigator, or treating physician)
- 8.5.1.7. Action taken as a result of the event, including but not limited to; no changes, dose interrupted, reduced, discontinued, etc. or action taken with regard to the event, i.e. no action or other intervention, etc.

8.5.2. Descriptions and grading scales found in the NCI Common Terminology Criteria for Adverse Events (CTCAE) version 4 will be utilized for AE reporting.

- 8.5.2.1. **An expected adverse event** is an event previously known or anticipated to result from participation in the research study or any underlying disease, disorder, or condition of the subject. The event is usually listed in the Investigator Brochure, consent form or research protocol.
- 8.5.2.2. **An unexpected adverse event** is an adverse event not previously known or anticipated to result from the research study or any underlying disease, disorder, or condition of the subject.
- 8.5.2.3. **Attribution** is the relationship between an adverse event or serious adverse event and the study drug. Attribution will be assigned as follows:
 - 8.5.2.3.1. Definite – The AE is clearly related to the study drug.
 - 8.5.2.3.2. Probable – The AE is likely related to the study drug.
 - 8.5.2.3.3. Possible – The AE may be related to the study drug.
 - 8.5.2.3.4. Unlikely – The AE is doubtfully related to the study drug.
 - 8.5.2.3.5. Unrelated – The AE is clearly NOT related to the study drug.
- 8.5.2.4. Protocol must specify if attribution is required for individual components of the treatment regimen or the treatment regimen as a whole.

8.5. ALL SAE attributed to the MAD will reported to the DSMB.

8.6 Data and Safety Monitoring Board: Any new significant finding that may affect the patient's willingness to continue in the study will be shared with patients. Immediately after the study is approved and before the first patient is enrolled, investigators will meet, develop and finalize all measurements/variables for the study. Each patient, once being enrolled, will be provided a unique id from the study and their personal information, such as name, SSN, address, phone number and DOB, will be de-identified whenever necessary to the researchers. Data entry will be monitored regularly by the “Data Safety Monitoring Board” which is an independent group of experts who will advise the study investigators. The members of the DSMB serve in an individual capacity and provide their expertise and recommendations. Membership consists of persons independent of the investigators and any conflict of interest with the trial. Written documentation attesting to absence of conflict of interest is required. The DSMB includes experts in or representatives of the fields of relevant clinical expertise, and biostatistics. The DSMB will be provided feedback on a regular basis, including findings from adverse-event reports, and recommendations derived from data and safety monitoring, and members of the DSMB will have no personal or financial stake in the study. Interim reports will be prepared at least twice each year by the PI with the help of the study coordinator 1 month prior to DSMB

meeting for DSMB review. These reports will contain information about the accrual rate with projected completion date for the accrual phase, exclusion rates and reasons, pretreatment characteristics of patients accrued, compliance rate of treatment delivered with respect to the protocol prescription, and the frequency and severity of adverse events. All serious adverse events will be reported by the PI to the DSMB and IRB within 24 hours of knowledge of the occurrence. HIPAA confidentiality will be maintained during the phases of the trial including monitoring, preparation of interim results, review, and response to monitoring recommendations. Exceptions may be made under circumstances where there are serious adverse events or when it is deemed appropriate for patient safety. The DSMB will function in an advisory capacity and recommendations that emanate from monitoring activities will be reviewed by the responsible official (the principal investigator) and addressed.

8.6.2 Responsibility of the DSMB: To approve the initiation of this clinical trial. After this approval and at periodic intervals during the course of the trial, the DSMB responsibilities are to periodically review and evaluate the accumulated study data for participant safety, study conduct and progress, and when appropriate, efficacy. Make recommendations to the study investigators and regulatory agencies (IRB, IBC, FDA, etc.) concerning the continuation, modification, or termination of the trial.

8.6.3 Responsibility of the PI: It is the responsibility of the study PI to ensure that the DSMB is apprised of all new safety information relevant to the study. This includes providing the DSMB with a copy of the study protocol in advance as well as providing all IRB/Regulatory Protocol revisions and all safety data reports.

8.6.4 Serious Adverse Events: (Please see section 8.4 for definitions of adverse events.) All serious and related adverse events will be reported immediately to the Chair and other members of the DSMB by the study sponsor or designee. The decision to meet by teleconference or on site to discuss the adverse event will be left to the discretion of the members of the DSMB. If the DSMB determines that the study procedures present a greater risk than expected, the board may recommend to the P.I. and the IRB that the study enrollment be suspended pending further evaluation.

8.6.4.1 Written Reports: Written reports should be sent to DSMB members prior to the meeting and should allow sufficient time for review. Written reports may consist of 2 separate parts:

8.6.4.2 Open Session Report: This report provides information on study conduct, such as accrual, appropriate demographic representation, baseline characteristics, protocol compliance, site performance, quality control, currency of follow-up. General (ungrouped) adverse events and toxicity issues will be included in the open report. Open Session reports will be distributed at least a week prior to a scheduled meeting to DSMB members, study investigators and other appropriate persons as directed by the DSMB.

8.6.4.3 Closed Session Report: This report may contain data on study outcomes, including safety data and efficacy data. Closed session reports are distributed on the same schedule, but only to DSMB members, the chairman of the IRB, and others as designated by the DSMB Chair. This report is confidential and marked accordingly.

8.6.4.4 Verbal Report: At the conclusion of the DSMB meeting, the DSMB should discuss its findings and recommendations with the study investigator and sponsor (or sponsor designee). The DSMB will issue a written summary report that identifies topics discussed by the DSMB and describes their individual findings, overall safety assessment and recommendations. The report should conclude with a recommendation to continue or terminate the study. The DSMB Chair or designee is responsible for drafting, circulating and obtaining approval from other DSMB members within 2 weeks of the meeting.

8.6.4.5 A final summary report: will be forwarded to the Study Sponsor and PI. The UCCI Regulatory Coordinator will forward the summary report to regulatory authorities as a part of the annual report unless immediate action is required.

8.6.4.6 Closed Session Report (optional):_The DSMB may also prepare confidential minutes that include details of closed session discussions. These meeting minutes are to be held in strict confidence and only accessible to DSMB members until such a time when the study is closed or the DSMB recommends early termination or in the event the minutes are requested by the FDA for participant safety reasons or for regulatory purposes.

8.6.4.7 Immediate Action Report: The DSMB Chair will notify the PI directly of any findings of a serious and immediate nature or recommendations to discontinue all or part of the trial. The report will be submitted to UCCI Regulatory Coordinator for appropriate dissemination to regulatory authorities. This will be done in order to identify significant adverse event trends, missing and incorrect inputs, and other outliers. A log file will be created and record any change/modification of data inputs for purpose of future inspection. Data files will be safely stored in the server of the cancer clinical trials office, with authorized access to researchers and staffs only; and protected by double firewalls from both UC Health and the University of Cincinnati Information Technology (UCIT). All active study patients are reviewed at the weekly study team meeting. Confidentiality will be maintained as much as possible, consistent with applicable regulations. Names of participants or identifying material will not be released without patient permission, except when such release is required by law. No patient's name or identifying information will be released in any publication or presentation. Records are maintained according to current legal requirements, and are made available for review according to the requirements of the Food and Drug Administration (FDA) or other authorized user, only under guidelines established by the Federal Privacy Act.

